13.6 Stipends for Participation

Subjects may be provided with a stipend according to local practice to compensate for the time and travel required for study visits and procedures.

## **List of Abbreviations**

AE	Adverse Event
AR	Adverse Reaction
BL	Blood Sample
CBER	Center for Biologics Evaluation and Research
CDC	Centers for Disease Control and Prevention
CI	Confidence Interval
CSR	Clinical Study Report
dil	Dilution
eCRF	Electronic Case Report Form
FAS	Full Analysis Set
FDA	Food and Drug Administration
GBS	Guillain-Barré Syndrome
HA	Hemagglutinin
HAI	Hemagglutination Inhibition
LLOQ	Lower Limit of Quantification
MD	Missing Data
MedDRA	Medical Dictionary for Regulatory Activities
PPAS	Per-Protocol Analysis Set
PT	Preferred Term
RCDC	Reverse Cumulative Distribution Curve
SAE	Serious Adverse Event
SafAS	Safety Analysis Set
SAP	Statistical Analysis Plan
SD	Standard Deviation
SOC	System Organ Class
ULOQ	Upper Limit of Quantification
WHO	World Health Organization

## 1 Introduction

This is a trial using the 2017–2018 formulations of quadrivalent inactivated influenza vaccine (Fluzone® Quadrivalent, Influenza Vaccine) and high-dose trivalent inactivated influenza vaccine (Fluzone® High-Dose, Influenza Vaccine). Fluzone Quadrivalent vaccine contains 4 influenza strains (A/H1N1, A/H3N2, and 2 B strains [1 each from the Victoria and Yamagata lineages]). Fluzone High-Dose vaccine contains 60 µg hemagglutinin (HA) per virus strain per dose, which is 4 times the amount of HA per strain per dose in Fluzone Quadrivalent vaccine. It was developed for use in the elderly to elicit enhanced immune responses against influenza through the use of higher antigen content.

During this study, Fluzone Quadrivalent or Fluzone-High-Dose vaccine will be administered in accordance with the age indications and guidance specified in the respective Prescribing Information for each vaccine.

The objectives of this study are to describe the safety and immunogenicity of Fluzone Quadrivalent vaccine in children 6 to <36 months and 3 to < 9 years of age, and in adults 18 to < 65 years of age, and to describe the safety and immunogenicity of Fluzone High-Dose vaccine in adults ≥ 65 years of age. An additional objective of the study is to submit sera from selected subjects to the Center for Biologics Evaluation and Research (CBER) for further analysis by the World Health Organization (WHO), the Centers for Disease Control and Prevention (CDC), and the Food and Drug Administration (FDA) to support formulation recommendations for subsequent influenza vaccines.

Fluzone Quadrivalent and Fluzone High-Dose vaccines are registered internationally. In the past, annual clinical study reports (CSRs) have been requested by certain national health authorities to demonstrate the safety and immunogenicity of Fluzone (trivalent) and Fluzone Quadrivalent vaccines in support of their registration outside the United States. The CSR for the trial described herein will be used to honor requests for information regarding the safety and immunogenicity of the vaccines evaluated in this trial, as appropriate.

## 2 Trial Objectives

### 2.1 Observational Objectives

#### 2.1.1 Safety

To describe the safety of the 2017–2018 formulation of Fluzone Quadrivalent vaccine in children 6 to <36 months of age and 3 to < 9 years of age, and in adults 18 to < 65 years of age, and the safety of the 2017–2018 formulation of Fluzone High-Dose vaccine in adults ≥ 65 years of age.

The endpoints for the observational safety objective are presented in Section 4.3.1.2.

### **2.1.2 Immunogenicity**

To describe the immunogenicity of the 2017–2018 formulation of Fluzone Quadrivalent vaccine in children 6 to <36 months of age, 3 to < 9 years of age, and in adults 18 to < 65 years of age, and the immunogenicity of the 2017–2018 formulation of Fluzone High-Dose vaccine in adults  $\geq$  65 years of age.

The endpoints for the observational immunogenicity objective are presented in Section 4.3.2.1.

### **2.1.3 Serum Collection**

To submit available sera from approximately 120 subjects (30 subjects from each age group) to CBER for further analysis by the WHO, the CDC, and the FDA to support formulation recommendations for subsequent influenza vaccines.

There are no endpoints for the serum collection objective.

## **3 Description of the Overall Trial Design and Plan**

### **3.1 Trial Design**

### **3.2 Trial Plan**

This is a Phase IV, multi-center, open-label study of a planned 240 subjects to describe the safety and immunogenicity of Fluzone Quadrivalent vaccine in children 6 months to < 9 years of age, adults 18 to < 65 years of age, and to describe the safety and immunogenicity of Fluzone High-Dose vaccine in adults  $\geq$  65 years of age. Each subject will be assigned to the appropriate age group based on the subject's age at the time of enrollment. An approximately equal number of subjects from each group will be enrolled at each site.

- Group 1: Children 6 to < 36 months of age assigned to receive a 0.25-mL pediatric dose of Fluzone Quadrivalent vaccine (60 subjects planned)
- Group 2: Children 3 to < 9 years of age assigned to receive a 0.5-mL dose of Fluzone Quadrivalent vaccine (60 subjects planned)
- Group 3: Adults 18 to < 65 years of age assigned to receive a 0.5-mL dose of Fluzone Quadrivalent vaccine (60 subjects planned)
- Group 4: Adults  $\geq$  65 years of age assigned to receive a 0.5-mL dose of Fluzone High-Dose vaccine (60 subjects planned)

All subjects will receive an intramuscular dose of their assigned vaccine during Visit 1. For subjects 6 months to < 9 years of age for whom 2 doses of influenza vaccine are recommended per guidance from the Advisory Committee on Immunization Practices, a second dose of the same volume of Fluzone Quadrivalent vaccine as the first dose will be administered at Visit 2 (28 [window, 28–35] days after Visit 1).

Subjects 6 months to < 9 years of age (Group 1 and Group 2): blood specimens will be obtained from all subjects prior to the first vaccination and 28 (window, 28–35) days following the final vaccination (Visit 2 for subjects receiving 1 dose; Visit 3 for subjects receiving 2 doses) and assayed for immunogenicity. Solicited adverse reaction (AR) information will be collected for 7 days after each vaccination. Unsolicited non-serious adverse event (AE) and serious adverse event (SAE) information will be collected from Visit 1 to Visit 2 for subjects receiving 1 dose or from Visit 1 to Visit 3 for those subjects receiving 2 doses.

Subjects ≥ 18 years of age (Group 3 and Group 4): blood specimens will be obtained from all subjects prior to vaccination and 21 (window, 21–28) days post-vaccination (Visit 2). Solicited AR information will be collected for 7 days after vaccination. Unsolicited non-serious AE and SAE information will be collected from Visit 1 to Visit 2.

***Pregnancy Testing***

A urine human chorionic gonadotropin pregnancy test or a serum pregnancy test supplied by Sanofi Pasteur will be used to test females of child-bearing potential for pregnancy prior to vaccination. Subjects will not participate in the study if the initial pregnancy test is positive.

**Table 3.1: Study Procedures**

**Trial Flow Chart for Subjects 6 Months to < 9 Years of Age: 2 or 3 Visits, 1 or 2 Vaccinations**

Visit Number	All Subjects		Subjects Receiving 1 Dose of Influenza Vaccine	Subjects Receiving 2 Doses of Influenza Vaccine		
	Visit 1	Telephone Contact		Visit 2	Telephone Contact	Visit 3
Trial Timelines	Day 0	Visit 1 + 8 days	Visit 1 + 28 days	Visit 1 + 28 days	Visit 2 + 8 days	Visit 2 + 28 days
Time Windows	--	+ 8 to 10 days	+ 28 to 35 days	+ 28 to 35 days	+ 8 to 10 days	+ 28 to 35 days
Informed consent/assent a	X					
Inclusion & exclusion criteria	X					
Demographic data	X					
Medical history	X					
Influenza vaccination history	X					
History-directed physical examination	X			X		
Temperature b	X			X		
Review contraindications for vaccination				X		
Allocation of subject number	X					
Blood sample (BL) c	BL1		BL2			BL2
Vaccination d	X			X		
Immediate surveillance (20 minutes)	X			X		
Diary card (DC) provided	DC1			DC2		
Telephone contact e		X			X	
Diary card reviewed and collected			DC1	DC1		DC2
Interim history			X	X		X
Termination record f			X			X
Serious adverse events	To be reported throughout the study period					

a Informed consent form will be signed and dated by parent(s) or guardian(s) for subjects 6 months to < 9 years of age and assent form will be signed and dated by subjects 7 to < 9 years of age.

b The preferred route for this study is rectal for subjects 6 to < 36 months of age, and oral for subjects 3 to < 9 years of age. The axillary route may be used when a rectal or oral temperature cannot be obtained.

c A blood sample, approximately 5 mL, will be collected from all subjects at Visit 1, prior to vaccination, and at either Visit 2 (for subjects receiving 1 influenza vaccine dose) or at Visit 3 (for subjects receiving 2 influenza vaccine doses).

- d One or 2 doses of influenza vaccine will be administered per guidance from the Advisory Committee on Immunization Practices in effect during the study. If 2 doses of influenza vaccine are indicated, 1 dose will be administered during Visit 1 and the second dose (same 0.25-mL or 0.5-mL volume of Fluzone Quadrivalent vaccine as administered at Visit 1) will be administered approximately 28 days later during Visit 2.
- e The subject's parent/guardian will be contacted by telephone on Day 8 (window, Days 8–10) after vaccination as a reminder to complete the diary card and to bring it with them to the next visit.
- f The termination form will be completed at Visit 2 for subjects receiving 1 dose of influenza vaccine or at Visit 3 for subjects receiving 2 doses of influenza vaccine.

**Trial Flow Chart for Subjects  $\geq 18$  Years of Age: 2 Visits, 1 Vaccination**

Visit Number	Visit 1	Telephone Contact	Visit 2
Trial Timelines	Day 0	Visit 1 + 8 days	Visit 1 + 21 days
Time Windows	--	+ 8 to 10 days	+ 21 to 28 days
Informed consent	X		
Inclusion & exclusion criteria	X		
Demographic data	X		
Medical history	X		
Influenza vaccination history (previous season)	X		
History-directed physical examination	X		
Temperature a	X		
Urine or serum pregnancy test b			
Allocation of subject number	X		
Blood sample (BL) c	BL1		BL2
Vaccination	X		
Immediate surveillance (20 minutes)	X		
Diary card (DC) provided	X		
Telephone contact d		X	
Diary card reviewed and collected			X
Termination record			X
Serious adverse events	To be reported throughout the study period		

a The preferred route for this trial for subjects  $\geq 18$  years of age is oral.

b Only for women of child-bearing potential.

c A blood sample, approximately 10 mL, will be collected at Visit 1 and Visit 2.

d Subjects will be contacted via telephone on Day 8 (window, Days 8–10) as a reminder to complete the diary card and to bring it with them to Visit 2

## 4 Endpoints and Assessment Methods

### 4.1 Primary Endpoints and Assessment Methods

#### 4.1.1 Safety

There are no primary objectives for safety.

#### 4.1.2 Immunogenicity

There are no primary objectives for immunogenicity.

#### 4.1.3 Efficacy

No clinical efficacy data will be obtained in the trial.

### 4.2 Secondary Endpoints and Assessment Methods

There are no secondary objectives in this study.

### 4.3 Observational Endpoints and Assessment Methods

#### 4.3.1 Safety

The observational safety objective is presented in Section 2.1.1.

##### 4.3.1.1 Safety Definitions

The following definitions are taken from the International Conference on Harmonisation E2A Guideline for Clinical Safety Data Management: Definitions and Standards for Expedited Reporting.

##### *Adverse Event:*

An AE is any untoward medical occurrence in a patient or clinical investigation subject administered a pharmaceutical product and which does not necessarily have to have a causal relationship with this treatment. An AE can therefore be any unfavorable and unintended sign (including an abnormal laboratory finding, for example), symptom or disease temporally associated with the use of a medicinal product, whether or not considered related to the medicinal product.

Therefore an AE may be:

- A new illness
- The worsening of a concomitant illness
- An effect of the vaccination, including the comparator

- A combination of the above

All AEs include serious and non-serious AEs.

Surgical procedures are not AEs; they are the action taken to treat a medical condition. It is the condition leading to the action taken that is the AE (if it occurs during the study period).

Pre-existing medical conditions are not to be reported as AEs. However, if a pre-existing condition worsens in frequency or intensity, or if in the assessment of the treating physician there is a change in its clinical significance, this change should be reported as an AE (exacerbation). This applies equally to recurring episodes of pre-existing conditions (e.g., asthma) if the frequency or intensity increases post-vaccination.

***Serious Adverse Event:***

*Serious* and *severe* are not synonymous. The term *severe* is often used to describe the intensity of a specific event as corresponding to Grade 3. This is not the same as *serious* which is based on patient/event outcome or action criteria usually associated with events that pose a threat to a patient's life or functioning. Seriousness, not severity, serves as a guide for defining regulatory reporting obligations.

An SAE is any untoward medical occurrence that at any dose

- Results in death
- Is life-threateninga
- Requires inpatient hospitalization or prolongation of existing hospitalizationb
- Results in persistent or significant disability/incapacityc
- Is a congenital anomaly/birth defect
- Is an important medical eventd

---

a The term “life-threatening” refers to an event in which the subject was at risk of death at the time of the event; it does not refer to an event which hypothetically might have caused death if it were more severe.

b All medical events leading to hospitalizations will be recorded and reported as SAEs, with the exception of: hospitalization planned before inclusion into the study or out-patient treatment with no hospitalization.

c “Persistent or significant disability or incapacity” means that there is a substantial disruption of a person’s ability to carry out normal life functions.

d Medical and scientific judgment should be exercised in deciding whether expedited reporting is appropriate in other situations, such as important medical events that may not be immediately life-threatening or result in death or hospitalization but may jeopardize the health of the subject or may require intervention to prevent one of the other outcomes listed in the definition above. These should also usually be considered serious. Examples of such events include allergic bronchospasm requiring intensive treatment in an emergency room or at home, blood dyscrasias or convulsions that do not result in inpatient hospitalization, the development of drug dependency or drug abuse, or new-onset diabetes or autoimmune disease.

Additionally, the following important medical events are to be considered as SAEs

New onset of Guillain-Barré syndrome (GBS), encephalitis/myelitis (including transverse myelitis), neuritis (including Bell's palsy, optic neuritis, and brachial neuritis), thrombocytopenia, vasculitis, convulsions (including febrile convulsions [children only]), and anaphylaxis or other hypersensitivity/allergic reactions.

***Adverse Reaction:***

All noxious and unintended responses to a medicinal product related to any dose should be considered ARs.

(The phrase “responses to a medicinal product” means that a causal relationship between a medicinal product and an AE is at least a reasonable possibility)

***Unexpected Adverse Reaction:***

An unexpected AR is an AR, the nature or severity of which is not consistent with the applicable product information (e.g., Investigator's Brochure for an unapproved investigational medicinal product).

The following additional definitions are used by Sanofi Pasteur:

***Solicited Reaction:***

A solicited reaction is an event that is prelisted in the electronic case report form (eCRF). The assessment of these AEs post-vaccination is mandatory. A solicited reaction is defined by a combination of:

- Symptom and
- Onset post-vaccination

Examples of solicited reactions include injection site pain from Day 0 through Day 7 post-vaccination, or headache from Day 0 through Day 7.

A solicited reaction is therefore an AR observed and reported under the conditions (symptom and onset) prelisted (i.e., solicited) in the eCRF and considered as related to vaccination.

***Unsolicited Adverse Event/Adverse Reaction:***

An unsolicited AE is an observed AE that does not fulfill the conditions prelisted in the eCRF in terms of diagnosis and/or onset post-vaccination (i.e., excluding solicited reactions). For example, if headache from Day 0 through Day 7 is a solicited reaction (i.e., prelisted in the eCRF), then a headache starting on Day 7 is a solicited reaction, whereas headache starting on Day 8 post-vaccination is an unsolicited AE.

Unsolicited non-serious AEs, by definition, do not include SAEs.

**Injection Site Reaction:**

An injection site reactiona is an AR at and around the injection site. Injection site reactions are commonly inflammatory reactions.

**Systemic Adverse Event:**

Systemic AEs are all AEs that are not injection site reactions. They therefore include systemic manifestations such as headache, fever, as well as localized or topical manifestations that are not associated with the vaccination site, e.g., erythema that is localized but that is not at the injection site).

**Adverse Events of Special Interest:**

Adverse events of special interest are AEs that are considered by the Sponsor to be relevant for the monitoring of the safety profile of the investigational vaccine.

#### 4.3.1.2 Safety Endpoints

The observational endpoints for the evaluation of safety are:

- 1) Occurrence, nature (Medical Dictionary for Regulatory Activities [MedDRA] preferred term [PT]), duration, intensity, and relationship to vaccination of any unsolicited systemic AEs reported in the 20 minutes after vaccination.
- 2) Occurrence, time to onset, number of days of occurrence, intensity, action taken, and whether the reaction led to early termination from the study, of solicited injection site reactions (prelisted in the subject's diary card and eCRF) occurring from Day 0 through Day 7 after vaccination.
- 3) Occurrence, time to onset, number of days of occurrence, intensity, action taken, and whether the reaction led to early termination from the study, of solicited systemic reactions (prelisted in the subject's diary card and eCRF) occurring from Day 0 through Day 7 after vaccination.
- 4) Occurrence, nature (MedDRA PT), time to onset, duration, intensity, action taken, relationship to vaccination (for systemic AEs only), and whether the event led to early termination from the study, of unsolicited AEs from Visit 1 through Visit 2 for subjects receiving 1 dose or from Visit 1 through Visit 3 for subjects receiving 2 doses.
- 5) Occurrence, nature (MedDRA PT), time to onset, seriousness criteria, relationship to vaccination, outcome, and whether the SAE led to early termination from the study, of SAEs from Visit 1 through Visit 2 for subjects receiving 1 dose or from Visit 1 through Visit 3 for subjects receiving 2 doses.

Adverse events of special interest will be captured as SAEs. These include new onset of GBS, encephalitis/myelitis (including transverse myelitis), neuritis (including Bell's palsy, optic neuritis, and brachial neuritis), thrombocytopenia, vasculitis, convulsions (including febrile convulsions [children only]), and anaphylaxis or other hypersensitivity/allergic reactions from Visit 1 through

---

a All injection site AEs are considered to be related to vaccination and therefore are all *injection site reactions*.

Visit 2 for subjects receiving 1 dose of vaccine, or from Visit 1 through Visit 3 for subjects receiving 2 doses of vaccine.

#### **4.3.1.3 Safety Assessment Methods**

See Section 9.3.1.3 of the protocol version 1.0, 24 April 2017.

#### **4.3.2 Immunogenicity**

The observational immunogenicity objective is presented in Section 2.1.2.

##### **4.3.2.1 Immunogenicity Endpoints**

Immunogenicity will be evaluated in all subjects by analyzing sera collected prior to vaccination on Day 0 (Visit 1) and after final vaccination (28 [window, 28–35] days post-final vaccination for subjects 6 months to < 9 years of age [Visit 2 for subjects receiving 1 dose; Visit 3 for subjects receiving 2 doses]; or 21 [window, 21–28] days post-vaccination for subjects  $\geq$  18 years of age) using the hemagglutination inhibition (HAI) assay technique.

For each influenza vaccine strain (i.e., 3 strains for Fluzone High-Dose vaccine [a trivalent vaccine] and 4 strains for Fluzone Quadrivalent vaccine), HAI assay titers at pre-vaccination (Day 0) and after the final vaccination will be determined in duplicate.

The derived endpointsa are:

- Geometric means of HAI assay titers at pre-vaccination and post-final vaccination
- Ratios of post-final vaccination titers divided by pre-vaccination titers
- Seroprotection: a titer  $\geq$  40 (1/dilution [dil]) at pre-vaccination and at post-final vaccination
- Seroconversion: either a pre-vaccination titer  $<$  10 (1/dil) and a post-final vaccination titer  $\geq$  40 (1/dil), or a pre-vaccination titer  $\geq$  10 (1/dil) and a  $\geq$  4-fold increase in post-final vaccination titer

##### **4.3.2.2 Immunogenicity Assessment Methods**

See Section 9.3.2.2 of the protocol for immunogenicity assessment methods.

#### **4.3.3 Efficacy**

No clinical efficacy data will be obtained in the trial.

---

a Post-final vaccination in each of the derived endpoints is defined as 28 (window, 28–35) days post-final vaccination for subjects 6 months to < 9 years of age, and 21 (window, 21–28) days post-vaccination for subjects  $\geq$  18 years of age

## 4.4 Derived Endpoints: Calculation Methods

### 4.4.1 Safety

#### 4.4.1.1 Solicited Reactions

##### 4.4.1.1.1 Daily Intensity

All daily intensities will be derived from daily records for solicited reactions according to the following classification: None, Grade 1, Grade 2, Grade 3, or Missing.

For the derivation of daily intensities, the following sequential steps will be applied:

- 1) For solicited reactions (except fever/pyrexia) for which an Investigator records their presence as “No” and for which all daily records are missing, all daily intensities will be derived as None
- 2) For a temperature with partially missing data (MD) after the decimal point, the data will be analyzed by replacing “MD” with zero. For example, a “39.MD°C” daily temperature will be considered as “39.0°C” in the analysis
- 3) For non-measurable solicited reactions, daily intensities will correspond to daily records reported in the clinical database. For measurable solicited reactions, the daily measurements reported in the clinical database will be converted based upon the intensity scales defined in the protocol; this assumes a reaction that is too large to measure (non-measurable, “NM”) is Grade 3

Note: The maximum intensity during the ongoing period will be derived from the record of the maximum intensity/measurement after the end of the solicited period following the rule described above.

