12.3 Handling of Missing Data and Outliers

12.3.1 Safety

No imputation of missing data will be conducted. All subjects with safety data and all safety data recorded in the eCRFs will be included in the safety analyses. No search for outliers will be performed.

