##### 4.4.1.1.3 Presence

Presence will be derived from the maximum overall intensity during the period considered:

None: No presence

Grade 1, Grade 2, or Grade 3: Presence

Missing: Missing presence

Subjects with at least 1 non-missing presence for a specific endpoint will be included in the analysis. Conversely, those with all missing presence will not be included in the analysis of the endpoint.

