#### 5.1.3.1 Safety Analysis

The safety analysis will report the occurrence of solicited reactions and the incidence of unsolicited AEs between Visit 1 and Visit 2 (or between Visit 1 and Visit 3 for those subjects receiving 2 doses).

To avoid any under-estimation of the incidences, the number of subjects with documented safety will be used as denominator for the frequencies.

- For solicited reactions, the denominator will be the total number of subjects who have non-missing data for the endpoint considered
- For unsolicited AEs, the denominator will be the total number of subjects who were vaccinated at the dose analyzed

The safety tables will be produced using a subject approach; i.e., number of subjects who experienced at least 1 safety event during a considered period.

The 2-sided 95% CIs for the percentages will be calculated using the exact binomial method (Clopper-Pearson method).

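### When all daily records are missing, the SAP uses an Investigator's No but has no rule for a Yes, so most solicited-reaction rates are too low whenever a Yes of this kind occurs

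*SAP*

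**What the plan says.** SAP 4.4.1.1.1 derives daily intensities in sequential steps. Step 1 begins "For solicited reactions (except fever/pyrexia) for which an Investigator records their presence as" No and ends "for which all daily records are missing, all daily intensities will be derived as None". Step 3 then takes intensity only from the daily entries: "For non-measurable solicited reactions, daily intensities will correspond to daily records reported in the clinical database", and measurable reactions are graded from the daily measurements. No step mentions an Investigator's Yes.

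SAP 4.4.1.1.3 derives presence from the maximum intensity. Grades 1 to 3 are presence, None is no presence, and the remaining case is "Missing: Missing presence". It adds that "those with all missing presence will not be included in the analysis of the endpoint".

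SAP 5.1.3.1 sets the denominator: "For solicited reactions, the denominator will be the total number of subjects who have non-missing data for the endpoint considered". It gives the reason: "To avoid any under-estimation of the incidences, the number of subjects with documented safety will be used as denominator for the frequencies".

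Protocol 12.3.1 says "No imputation of missing data will be conducted". It also says that the safety analyses will include every item of safety data entered in the eCRF.

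**The concern.** The same eCRF answer is treated differently according to its content. A No without daily records keeps the subject in the denominator as a non-reactor. A Yes without daily records removes the subject from numerator and denominator. A subject known to have reacted is lost, while a subject known not to have reacted is kept.

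This works against the SAP's stated wish not to under-estimate incidence, and against the protocol's statement that recorded safety data are included. It also differs from the cautious choices elsewhere in the SAP: a reaction too large to measure becomes Grade 3 (4.4.1.1.1), missing causality counts as related (5.3.1.2), and the worst case is taken across two doses (4.4.1.1.4 to 4.4.1.1.6).

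Solicited-reaction percentages with confidence intervals are a main output of this descriptive study, and SAP section 1 says the study report will be used to answer requests for safety information.

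**Working it through.** **Tracing the rules for one endpoint other than fever, all daily records missing**

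| Investigator's answer | Daily intensity | Maximum | Presence | In the analysis? |
|---|---|---|---|---|
| No | None (step 1) | None | No | Yes, as a non-reactor |
| Yes | Missing (step 3) | Missing | Missing | No |

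The asymmetry does not arise for fever, because step 1 excepts it. It does not arise for partly missing records either, because one graded day is enough for presence.

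**Does a Yes imply at least Grade 1?** In protocol Tables 9.1 and 9.2, erythema and swelling in children are Grade 1 from any size above 0 mm. Pain, tenderness and the solicited systemic reactions other than fever have no lower threshold that a present reaction could fail to reach. In Table 9.3, for subjects 18 years and older, Grade 1 erythema and swelling start at 25 mm, so a Yes without a measurement may fall below Grade 1.

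**Size where a Yes implies at least Grade 1.** The documents give no rate to reproduce and no expected number of affected subjects. Let
- N = 60, the planned group size (SAP 5.5);
- x = subjects with a graded reaction (assumed 6, 18 or 30);
- k = subjects with Yes and no daily records (assumed).

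The remaining N − k − x subjects are non-reactors, by daily records or by step 1.

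Rate under the SAP = x/(N − k). Rate with each Yes counted = (x + k)/N.

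Difference = (x + k)/N − x/(N − k) = k(N − k − x)/[N(N − k)].

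This is never negative. It is positive when k is at least 1 and at least one analysed subject has no reaction.

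For k = 3, with exact 95% Clopper-Pearson intervals:

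| x | SAP rate | Yes counted | Difference |
|---|---|---|---|
| 6 | 6/57 = 10.5% (4.0 to 21.5) | 9/60 = 15.0% (7.1 to 26.6) | 3 × 51/(60 × 57) = 4.5 points |
| 18 | 18/57 = 31.6% (19.9 to 45.2) | 21/60 = 35.0% (23.1 to 48.4) | 3 × 39/(60 × 57) = 3.4 points |
| 30 | 30/57 = 52.6% (39.0 to 66.0) | 33/60 = 55.0% (41.6 to 67.9) | 3 × 27/(60 × 57) = 2.4 points |

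Over the same range of x, the difference is 0.8 to 1.5 points for k = 1 and 4.4 to 8.9 points for k = 6. For k = 0 it is zero.

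**Adult erythema and swelling.** Take N = 60, x = 6, and 3 subjects with an unmeasured Yes that was truly under 25 mm. The SAP gives 6/57 = 10.5%. The value that follows the grading scale is 6/60 = 10.0%. Counting every Yes gives 9/60 = 15.0%. Here dropping the Yes raises the rate slightly, and counting it overstates the rate.

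**The case against.** **The direction is not the same for every endpoint.** A reader might infer that the rule can only lower the solicited-reaction rates. The adult erythema and swelling example shows otherwise, so those two endpoints in Groups 3 and 4 are left out of the claim about direction.

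**Step 1 may not be imputation.** A reader might infer that step 1 breaches the protocol's rule against imputing safety data. The documents do not support that. Step 1 needs a recorded No, and using a recorded answer is not clearly imputation. It may reflect a form on which No leaves the daily fields blank; excepting fever, for which temperature is recorded daily, fits that reading. The eCRF is not in the documents, so this cannot be settled.

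**Deleting step 1 is not a safe way to restore symmetry.** If non-reactors are routinely entered as No with blank daily fields, deletion would exclude them and inflate the rates.

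**The SAP elsewhere prefers measurements to flags.** SAP 4.4.1.1.7 ignores the Investigator's ongoing flag because the measurement decides. A Yes does not fix a grade. That explains a missing grade, but not losing the reaction where any Yes is at least Grade 1.

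**SAP 5.3.1.4 provides a missing class for intensity.** It does not say that such solicited reactions count as present, and 4.4.1.1.3 excludes them specifically.

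**The case may be rare.** Sites ask about reactions at visits, chase unreturned diary cards, clarify incomplete entries and must explain missing data (protocol 5.1.4, 9.3.1.3, 11.1 and 13.2). This stands: the number may be small or zero. The same procedures also allow a Yes to be recorded with no daily entries, when a parent or subject reports a reaction only at interview.

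**The study is descriptive and the shift is small next to the intervals.** True for the counts illustrated, and it limits the weight of the point. Wide intervals do not justify dropping known reactors.

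**Conclusion.** The point holds in a bounded form. Reading SAP 4.4.1.1.1, 4.4.1.1.3 and 5.1.3.1 together, an Investigator's No without daily records is used and a Yes is not. Exclusion of the Yes is nowhere written as such; it follows because no rule retains it. It applies endpoint by endpoint and only when every daily record is missing.

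For all solicited reactions except fever, and except erythema and swelling in subjects 18 years and older, the reported incidence is biased downward if at least one such subject exists and at least one analysed subject has no reaction. For adult erythema and swelling the direction cannot be stated. The conflict is with the aim in SAP 5.1.3.1 and with the protocol 12.3.1 statement that recorded safety data are included.

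The size is unknown. The 2.4 to 4.5 points rest on an assumed 3 affected subjects in a group of 60, with 30 down to 6 graded reactors. It is worth correcting because the correction is simple, not because a large error has been shown.

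**What to change.** Keep step 1. Add to SAP 4.4.1.1.1 and 4.4.1.1.3 that an Investigator's Yes with all daily records missing counts as presence with intensity Missing, using the missing class in SAP 5.3.1.4, in both numerator and denominator.

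For erythema and swelling in subjects 18 years and older, show the rate with and without these subjects, because an unmeasured Yes may be under 25 mm.

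For each endpoint, report how many subjects fall under the No branch and how many under the Yes branch, so that the effect can be seen.

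The cost is a short addition to the SAP, a small change in the derivation program and one extra presentation for two adult endpoints. Some reactions will appear with a missing grade.
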